2.1 Overview

The HEALEY ALS Platform Trial is a perpetual multi-center, multi-regimen clinical trial evaluating the safety and efficacy of investigational products for the treatment of ALS. RGD evaluates the safety and efficacy of pridopidine administered orally at a dosage of 45 mg twice daily (BID) vs. placebo. The RGD RSA describes the nature of the intervention and its mechanism of action, the mode and frequency of administration, additional eligibility criteria beyond those specified in the Master Protocol, additional enrollment procedures, and additions and modifications of safety and efficacy assessments relative to those outlined in the Master Protocol.

2.2 Study Objectives

Primary Efficacy Objective:

- To evaluate the efficacy of pridopidine as compared to placebo on ALS disease progression.

Secondary Efficacy Objectives:

- To evaluate the effect of pridopidine on selected secondary measures of disease progression, including survival

Safety Objectives:

- To evaluate the safety of pridopidine in ALS patients.

Exploratory Efficacy Objectives:

- To evaluate the effect of pridopidine on selected biomarkers and endpoints.
- To explore plasma pharmacokinetics (PK) of pridopidine and its metabolites.
- To explore relationship between PK of pridopidine and pharmacodynamic endpoints.

2.3 Study Population

In addition to eligibility criteria specified in the Master Protocol, participants in RGD must not have a confirmed prolonged Fridericia-corrected QT (QTcF) interval or clinically significant heart disease or selected cardiac abnormalities, must not have used selected prohibited medications within 4 weeks prior to the Regimen-specific Screening Visit, must not currently use selected medications above specified dosage thresholds at the time of the Regimen-specific Screening Visit, and must not have a history of allergy to any ingredient of study drug. Detailed criteria are specified in the Master Protocol and the RGD RSA.

Participants will be recruited from approximately 60 centers located throughout the US that are part of the Northeast ALS (NEALS) Consortium.

2.4 Participant Flow

Participants in RGD follow the consenting, Master screening, regimen assignment, regimen-specific screening, randomization to active or placebo treatment, and follow-up procedures and timing described in the M-SAP. Detailed descriptions of study procedures and timing are specified in the Master Protocol and the RGD RSA.

2.5 Regimen Allocation

Participants in RGD are those determined eligible for Master Protocol-level inclusion and exclusion criteria and randomly assigned to RGD, stratified by use of riluzole, edaravone, both, or neither at the time of screening for the Master Protocol. Details of regimen assignment are described in the Platform Trial Regimen Assignment Plan.

2.6 Treatment Allocation

Participants in RGD are randomly allocated in a 3:1 ratio to pridopidine 45 mg BID or placebo treatment based on a pre-specified permuted-block randomization schedule, stratified by use of riluzole, edaravone, both, or neither at the time of screening for the Master Protocol.

2.7 Treatment Administration

Pridopidine and placebo are supplied as capsules for oral administration. Each capsule of active study drug contains 45 mg of pridopidine plus silicified microcrystalline cellulose and magnesium stearate as inactive excipients.

The first dose of study drug should be administered while in the office/clinic on the day of the Baseline Visit after all visit assessments are complete except for post-dose ECG recordings.

From the Baseline Visit to the end of Week 2, participants should take one capsule of study drug orally once daily in the morning (the QD dose schedule). Starting at the beginning of Week 3 and throughout the remainder of the study, participants should take one capsule of study drug twice daily, once in the morning and once in the afternoon (approximately 7 to 10 hours after the morning dose; the BID dose schedule).

After the 2-week up-titration period, participants who are unable to tolerate the BID dose schedule should reduce their dosage to the QD dose schedule for one week. If a participant is tolerant of the QD dose schedule, then they should resume the BID dose schedule. If the participant cannot tolerate the second increase to the BID dose schedule, then they should continue on the QD dose schedule for the remainder of the study.

Additional details of treatment administration are described in the RGD RSA.

2.8 Allocation Concealment

Allocation concealment is the same as described in the M-SAP. Both active and placebo formulations of study drug are identical in appearance.

2.9 RGD Schedule of Activities (SoA)

Activity	MP Scrn ¹	RGD Scrn ¹	Base-line	Week 2	Week 4 ¹⁴	Week 8 ¹⁹	Week 12	Week 16 ¹⁹	Week 20	Week 24/E T ^{14, 22}	Final Call ¹¹
	Clinic	Clinic	Clinic	Phone	Clinic	Clinic	Phone	Clinic	Phone	Clinic	Phone
	-42d to -1d	-41d to 0d	Day 0	Day 14 ±3	Day 28 ±7	Day 56 ±7	Day 84 ±3	Day 112 ±7	Day 140 ±3	Day 168 ±7	28d ±3 ALD
Written Informed Consent ²	X	X									
Inclusion/Exclusion Review	X	X ³									
ALS & Medical History	X										
Demographics	X										
Physical Examination	X										
Neurological Exam	X										
Vital Signs ⁴	X		X		X	X		X		X	
Slow Vital Capacity	X ²⁰		X			X		X		X	
Home Spirometry	X ²⁰		X			X		X		X	
Muscle Strength Assessment			X			X		X		X	
ALSFRS-R	X		X		X	X	X	X	X	X	
ALSAQ-40			X							X	
CNS Bulbar Function Scale			X			X		X		X	
CNS Lability Scale			X			X		X		X	
12-Lead ECG	X	X ¹⁵	X ¹⁶		X ¹⁶					X ^{15, 16, 17}	

Activity	MP Scrn ¹	RGD Scrn ¹	Base-line	Week 2	Week 4 ⁴	Week 8 ¹⁹	Week 12	Week 16 ¹⁹	Week 20	Week 24/E T ^{14, 22}	Final Call ¹¹
	Clinic	Clinic	Clinic	Phone	Clinic	Clinic	Phone	Clinic	Phone	Clinic	Phone
	-42d to -1d	-41d to 0d	Day 0	Day 14 ±3	Day 28 ±7	Day 56 ±7	Day 84 ±3	Day 112 ±7	Day 140 ±3	Day 168 ±7	28d ±3 ALD
Clinical Safety Labs ^{5, 21}	X		X		X	X		X		X	
Biomarker Blood Collection ²¹			X			X		X		X	
Plasma PK collection ²¹					X					X	
Biomarker Urine Collection			X			X		X		X	
DNA Collection ^{7, 21} (optional)			X								
CSF Collection (optional)			X					X ¹³			
Concomitant Medication Review	X	X	X	X	X	X	X	X	X	X	
Adverse Event Review ⁶	X	X	X	X	X	X	X	X	X	X	X
Suicidality C-SSRS			X		X	X		X		X	
Install Smartphone App ²³			X								
Voice Recording ⁹			X		X	X		X		X	
Uninstall Smartphone App										X	
Randomization to Regimen	X										
Randomization within Regimen			X								
Administer/Dispense Study Drug			X ⁸		X ¹⁸	X		X		X ^{10, 18}	
Drug Accountability/Compliance				X ²⁴	X	X	X ²⁴	X	X ²⁴	X	
Exit Questionnaire										X	
Vital Status Determination ¹²										X	

Abbreviations: ALD = after last dose, ALS = amyotrophic lateral sclerosis, ALSAQ-40 = ALS Assessment Questionnaire, ALSFRS-R = ALS Functional Rating Scale Revised, CSF = cerebrospinal fluid, C-SSRS = Columbia-Suicide Severity Rating Scale, d = day, DNA = deoxyribonucleic acid, ECG = electrocardiogram, MP = Master Protocol, RGD = the pridopidine regimen, Scrn = Screening Visit.

¹ Master Protocol Screening procedures must be completed within 42 days to 1 day prior to the Baseline Visit. The Regimen-Specific Screening Visit and Baseline Visit should be combined, if possible.

² During the Master Protocol Screening Visit, participants will be consented via the Platform Trial informed consent form (ICF). After a participant is randomized to a regimen, participants will be consented a second time via the regimen-specific ICF.

³ At the Regimen Specific Screening Visit, participants will have regimen-specific eligibility criteria assessed.

⁴ Vital signs include weight, systolic and diastolic pressure, respiratory rate, heart rate and temperature. Height measured at Master Protocol Screening Visit only.

⁵ Clinical safety labs include hematology (CBC with differential), complete chemistry panel, thyroid function and urinalysis. Serum pregnancy testing will occur in women of child-bearing potential at the Master Protocol Screening Visit and as necessary during the study. Pregnancy testing is only repeated as applicable if there is a concern for pregnancy.

⁶ Adverse events that occur after signing the master protocol consent form will be recorded.

- ⁷ The DNA sample can be collected after Baseline Visit if a baseline sample is not obtained or the sample is not usable.
- ⁸ Administer first dose of IP only after Baseline Visit procedures are completed, except for the post-dose ECG.
- ⁹ In addition to study visits outlined in the SOA, participants will be asked to complete twice weekly voice recordings at home.
- ¹⁰ Drug will only be dispensed at this visit if the participant continues in the OLE.
- ¹¹ Participants will only have a Follow-Up Safety Call at this time if they *do not* continue on in the OLE. Participants who continue into OLE will have a Follow-Up Safety Call after their last dose of IP during the OLE period.
- ¹² Vital status, defined as a determination of date of death or death equivalent or date last known alive, will be determined for each randomized participant at the end of the placebo-controlled portion of their follow-up (generally the Week 24 Visit, as indicated). If at that time the participant is alive, his or her vital status should be determined again at the time of the last participant's last visit (LPLV) of the placebo-controlled portion of a given regimen. We may also ascertain vital status at later time points by using publicly available data sources as described in section 8.15 of the Master Protocol.
- ¹³ If the CSF collection is unable to be performed for logistical reasons, such as scheduling, at the Week 16 Visit, it may be performed at the Week 24 Visit.
- ¹⁴ If a participant's visit occurs in the morning, the participant should be instructed that the morning dose of study medication should not be taken, and the morning dose should be administered in-clinic 1-2 hours prior to the POST-DOSE ECG. If a participant's visit occurs in the afternoon, the participant should be instructed to take the morning dose immediately upon waking in the morning, and the second dose should be administered in-clinic 1-2 hours prior to the POST-DOSE ECG.
- ¹⁵ At the regimen-specific Screening visit (and Week 24 for participants enrolling in OLE), QTcF will be determined by the mean of three, 10-second recordings of a 12-Lead ECG (performed at least 1 minute a part) BEFORE IP administration. For participants on Nuedexta, the Nuedexta dose should be taken within 6 hours BEFORE the ECG, refer to the MOP for additional guidelines.
- ¹⁶ At Baseline and Week 4 (and Week 24 for participants enrolling in OLE) QTcF will be determined by a single 10-second 12-lead ECG, 1-2 hours AFTER IP administration. If stopping or monitoring rules are met, refer to Section 4.4. For participants on Nuedexta, the Nuedexta dose should be taken within 6 hours BEFORE the ECG, refer to the MOP for additional guidelines.
- ¹⁷ For participants that will NOT be enrolling into the OLE, QTcF will be determined by a single 10-second 12 lead ECG BEFORE administration of the IP. If stopping or monitoring rules are met, refer to Section 4.4. For participants on Nuedexta, the Nuedexta dose should be taken within 6 hours BEFORE the ECG, refer to the MOP for additional guidelines.
- ¹⁸ IP must be administered at Week 4 (and Week 24 for participants enrolling into the OLE) 1-2 hours prior to the POST-DOSE ECG.

¹⁹ Visit may be conducted via phone or telemedicine with remote services instead of in-person if this is needed to protect the safety of the participant due to a pandemic, or other reasons.

²⁰ If required due to pandemic-related restrictions, Forced Vital Capacity (FVC) performed by a Pulmonary Function Laboratory evaluator or with a study-approved home spirometer, or sustained phonation using a study approved method may be used for eligibility (Master Protocol Screening ONLY).

²¹ All blood draws should occur after the ECG is collected, or at least 1 hour prior to the ECG.

²² If participant's visit occurs in the morning, the participant should be instructed not to take the morning dose at home but rather in-clinic after the PRE-DOSE ECG.

If visit occurs in the afternoon, morning dose should be taken immediately upon waking in the morning and the second dose after the PRE-DOSE ECG.

²³ Two smartphone apps should be installed on the participant's phone, one to collect the voice recordings and one to collect home spirometry.

²⁴ Drug accountability will not be done at phone visits. A drug compliance check-in should be held during phone visits to ensure participant is taking drug per dose regimen and to note any report of missed doses.

3. General Considerations for Data Analysis

3.1 Statistical Software

Statistical software use for analyses is the same as described in the M-SAP.

3.2 Summary Statistics

Data summaries are the same as described in the M-SAP.

Summary statistics for time-to-event endpoints will include the percentage of subjects having the event and relevant percentiles of the survival curve depending on frequency of a given event.

Summary statistics for responder endpoints will include the percentage of responders.

3.3 Precision

Precision of reported results is the same as described in the M-SAP.

3.4 Transformations

Data transformations are the same as described in the M-SAP.

3.5 Multiplicity Adjustments

The primary endpoint will be tested first, and key secondary endpoints will be tested next in a fixed sequence with overall family-wise error rate controlled by a closed-testing procedure as indicated in Section 6.5.1 Hierarchical Testing below.

3.6 Missing Data

Handling of missing data is the same as described in the M-SAP except as indicated below. Mean imputation of any missing baseline covariates will impute after transformation for any transformed covariates. Clinic-based assessments that are missing due to COVID-19 restrictions or disruptions are considered missing at random.

Handling of missing data depends upon the type and pattern of missing data (monotone, non-monotone, deaths), the endpoint analyzed (ALSFRS-R, SVC, HHD, etc.), the method of analysis (continuous, time to event, responder), and the reason for missing data (related to lack of efficacy, related to tolerability, administrative reasons unrelated to lack of efficacy or tolerability, and unknown reasons).

Deaths are considered a special type of missing data.

For continuous analysis of all endpoints, the method described in the M-SAP for handling missing data will be followed.

For time-to-event analyses that depend on scheduled assessments, participants lacking any post-baseline assessment not due to death or disease progression will be censored at baseline and functionally omitted from the analysis. If data are missing not due to death, no imputation will be made for the primary analysis. As a sensitivity analysis, multiple imputations as described in Section 6.5.10 Placebo Multiple Imputation below will be used. All subjects who die, reach a death equivalent, or early terminate due to disease progression before reaching the pre-specified time-to-event will be considered as having the unfavorable event being analyzed (e.g., worsening by 1 or more points in bulbar subscale score) at the time of death, death equivalent or early termination, respectively.

For responder analysis, participants experiencing the unfavorable event (e.g., worsening in bulbar subscale score) are considered non-responders. All participants who die, reach a death equivalent, or early terminate due to disease progression will be considered non-responders. Data missing not due to death, death equivalent, or early terminate due to disease progression will be imputed under an assumption that data are conditionally missing at random (MAR). Under MAR, monotone missing data for participants will be imputed using available data from participants within the treatment group to which the participant was randomized. Sensitivity analyses based on multiple imputation under an assumption that data are missing not at random (MNAR) will be performed as described in the M-SAP.

4. Study Endpoints

4.1 Efficacy Endpoints

The primary efficacy endpoint is the same as described in the M-SAP.

The following secondary efficacy endpoints are adjusted for multiplicity and will be evaluated hierarchically:

- Time to first decline of 2 points or greater post baseline in the ALSFRS-R total score among participants in the FAS with bulbar dysfunction at baseline defined as an ALSFRS-R bulbar domain (Q1-Q3) score of less than 12,

- Proportion of participants experiencing no worsening in the ALSFRS-R bulbar domain (Q1-Q3) score from baseline through Week 24 among all participants in FAS,
- Rate of change in respiratory function as measured by slow vital capacity (SVC) maximum percent predicted from baseline through Week 24 among participants in FAS with bulbar dysfunction at baseline defined as an ALSFRS-R bulbar domain (Q1-Q3) score of less than 12,
- Time to first decline of 1-point or greater post baseline in the ALSFRS-R bulbar domain (Q1-Q3) score among all participants in FAS,
- Time to death or death equivalent through Week 24 among all participants in FAS.

Other Secondary Efficacy Endpoints (pre-specified non multiplicity adjusted non-hierarchical)

- Time to first decline of 2 points or greater post baseline in the ALSFRS-R total score among participants in FAS,
- Proportion of participants experiencing 5 points or less decline in the ALSFRS-R total score from baseline through Week 24 among all participants in FAS,
- Proportion of participants experiencing 5 points or less decline in the ALSFRS-R total score from baseline through Week 24 among all participants in FAS with baseline ALSFRS-R greater than or equal to 36 (Early in disease),
- Proportion of participants experiencing 5 points or less decline in the ALSFRS-R total score from baseline through Week 24 among all participants in FAS with bulbar dysfunction at baseline defined as an ALSFRS-R bulbar domain (Q1-Q3) score of less than 12,
- Rate of change in ALSFRS-R Total Score from baseline through Week 24 among participants in FAS with bulbar dysfunction at baseline defined as an ALSFRS-R bulbar domain (Q1-Q3) score of less than 12,
- Proportion of participants experiencing no or only a 1-point decline in the ALSFRS-R bulbar domain (Q1-Q3) score from baseline through Week 24 among participants in FAS with bulbar dysfunction at baseline defined as an ALSFRS-R bulbar domain (Q1-Q3) score of less than 12,
- Time to first decline of 1 or more points post baseline in the ALSFRS-R bulbar domain (Q1-Q3) score among participants in FAS with bulbar dysfunction at baseline defined as an ALSFRS-R bulbar domain (Q1-Q3) score of less than 12,
- Proportion of participants experiencing no worsening in the ALSFRS-R bulbar domain (Q1-Q3) score from baseline through Week 24 among all participants in FAS with delta-FRS slower than -0.75 points/month (slow progressors),
- Proportion of participants with ALSFRS-R bulbar domain (Q1-Q3) score greater than or equal to 9 (out of 12) at Week 24 among all participants in FAS with bulbar dysfunction at baseline defined as an ALSFRS-R bulbar domain (Q1-Q3) score of less than 12,

- Proportion of participants experiencing no worsening in the ALSFRS-R bulbar domain (Q1-Q3) score from baseline through Week 24 among all participants in FAS with baseline ALSFRS-R greater than or equal to 36 (Early in disease),
- Rate of change in CNS-BFS total score from baseline through Week 24 among all participants in FAS,
- Rate of change in CNS-BFS total score from baseline through Week 24 among participants in FAS with bulbar dysfunction at baseline defined as an ALSFRS-R bulbar domain (Q1-Q3) score of less than 12,
- Change in HHD upper extremity percentage from baseline through Week 24,
- Change in HHD lower extremity percentage from baseline through Week 24,
- Change in log transformed serum NfL from baseline through Week 24 among all participants in FAS,
- Change in log transformed serum NfL from baseline through Week 24 among participants in FAS with bulbar dysfunction at baseline defined as an ALSFRS-R bulbar domain (Q1-Q3) score of less than 12,
- Change in log transformed serum NfL from baseline through Week 24 among participants in FAS by NfL median baseline split (slow vs fast progressors),
- Rate of change in ALSFRS-R total score from baseline through Week 24 among participants in FAS who were not on Nuedexta at baseline,
- Rate of change in ALSFRS-R total score from baseline through Week 24 among participants in FAS who were not on Nuedexta at baseline and with bulbar dysfunction at baseline defined as an ALSFRS-R bulbar domain (Q1-Q3) score of less than 12,
- Rate of change in CNS-BFS total score from baseline through Week 24 among participants in FAS who were not on Nuedexta at baseline,
- Rate of change in CNS-BFS total score from baseline through Week 24 among participants in FAS who were not on Nuedexta at baseline and with bulbar dysfunction at baseline defined as an ALSFRS-R bulbar domain (Q1-Q3) score of less than 12,
- Proportion of participants experiencing no worsening in the CNS-BFS total score from baseline through Week 24 among all participants in FAS who were not on Nuedexta at baseline,
- Time to first increase of 5 points or more post baseline in the CNS-BFS total score among all participants in FAS who were not on Nuedexta at baseline, and
- Rate of change in ALSFRS-R total score from baseline through Week 24 among participants in FAS who were on Nuedexta at baseline.

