MAM	Mitochondria-associated membrane
MATE1	Multi Drug and Toxin Extrusion Protein 1
MATE2-K	Multi Drug and Toxin Extrusion Protein 2-K
MN	Motor Neuron
MOP	Manual of Procedures
mHTT	Mutant Huntingtin
NMJ	Neuromuscular Junction
OLE	Open Label Extension
OCT1	Organic Cation Transporter 1
OCT2	Organic Cation Transporter 2
QD	Once Daily
PD-LID	Parkinson's Disease-Levodopa Induced Dyskinesias
PET	Positron emission tomography
PO	By Mouth
PPK	Population Pharmacokinetic Model
PM	Poor Metabolizer

PY	Participant-Years
QTcF	Fridericia-corrected QT
RSA	Regimen-Specific Appendix
S1R	Sigma-1 Receptor
SAE	Serious Adverse Event
SI	Site Investigator
SOA	Schedule of Activities
SVC	Slow Vital Capacity
TDD	Total Daily Dose

REGIMEN-SPECIFIC APPENDIX (RSA) SUMMARY

Regimen-Specific Appendix D

For pridopidine 45 mg oral capsule administered twice daily (BID) or its matching placebo.

Rationale and RSA Design

The proposed study is based on cumulative preclinical and clinical studies that demonstrate that pridopidine acts primarily as a Sigma-1 Receptor (S1R) agonist and demonstrates neuroprotective properties mediated by S1R. The purpose of this study is to evaluate the effect of pridopidine 45 mg BID on ALS functional decline, specifically bulbar, upper and lower limb, and respiratory function in participants with ALS.

Allocation to Treatment Regimens

Participants must first be screened under the Master Protocol before they are randomized to a regimen.

As soon as pre-defined criteria for futility for the regimen are met, or the target number of randomized participants has been reached, enrollment will stop in the regimen.

Number of Planned Participants and Treatment Groups

The number of planned participants for this regimen is approximately 160.

There are 2 treatment groups for this regimen, active and placebo. Participants will be randomized in a 3:1 ratio to active treatment or placebo (i.e., 120 active: 40 placebo).

Planned Number of Sites

Research participants will be enrolled from approximately 60 centers across the US.

Treatment Duration

The maximum duration of the placebo-controlled treatment period is 24 weeks.

Follow-up Duration

At the conclusion of the 24-week placebo-controlled treatment period of the study, all participants will either schedule a 28-day follow up phone call and end their participation in the regimen or have the option to receive pridopidine in the Open Label Extension (OLE) period of the study.

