4.2.1 RSA Inclusion Criteria

There are no additional RSA Inclusion Criteria from those described in the Master Protocol.

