6.5.5 Responder Analysis

Analysis of responder endpoints will use logistic regression. The dependent variable will be whether the participant is a responder or not, while the independent variables will be treatment group, baseline ALSFRS-R score, site of onset (any bulbar vs. non-bulbar), riluzole use at baseline, edaravone use at baseline, and delta-FRS. A separate supportive analysis will include centered baseline serum NfL level as an additional covariate.

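### The responder endpoint of a bulbar score of at least 9 at Week 24 counts participants already below 9 at baseline, and the planned model does not adjust for baseline bulbar score, so the effect is attenuated and power is lost

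*SAP*

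**What the plan says.** SAP 4.1 defines response by the level reached at Week 24: "Proportion of participants with ALSFRS-R bulbar domain (Q1-Q3) score greater than or equal to 9 (out of 12) at Week 24 among all participants". The same bullet gives the population as FAS participants with "bulbar dysfunction at baseline defined as an ALSFRS-R bulbar domain (Q1-Q3) score of less than 12". The domain runs to 12, so baseline scores of 0 to 11 are all included. The endpoint sits in the list headed as outside the hierarchy and not adjusted for multiplicity.

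The supplied documents set no floor on the baseline bulbar score. RSA section 4.2.1 states: "There are no additional RSA Inclusion Criteria from those described in the Master Protocol".

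On analysis, SAP 6.5.5 says: "Analysis of responder endpoints will use logistic regression". Its independent variables are "treatment group, baseline ALSFRS-R score, site of onset (any bulbar vs. non-bulbar), riluzole use at baseline, edaravone use at baseline, and delta-FRS". The bulbar domain score at baseline is not among them. SAP 3.6 counts deaths, death equivalents and early terminations for progression as non-responders.

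On the expected course of disease, the RSA summary says: "The purpose of this study is to evaluate the effect of pridopidine 45 mg BID on ALS functional decline".

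**The concern.** The endpoint asks who still has a bulbar score of 9 or more at Week 24. A participant who enters at 8 or lower already fails that criterion and can pass it only by improving. In a trial of slowing decline, few will do so in either arm. They enlarge the denominator of both arms and say little about the drug.

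Elsewhere the SAP removes participants who already have the event or are not at risk of it:

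- Section 6.5.4 limits time to first bulbar dysfunction to a baseline score of 12.
- Section 5.12 excludes participants already ventilated, or already with a feeding tube, from those endpoints.
- Section 5.4 counts only muscles with non-zero strength at baseline for HHD0².

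The other bulbar responder endpoints in 4.1 and 4.2 are measured against the participant's own baseline, so they do not have this problem.

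At stake is the sensitivity of one pre-specified secondary endpoint that will be read as preservation of bulbar function.

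**Working it through.** The plan gives no response rate, effect size or power for this endpoint, so there is no figure to reproduce. Every input below that is not a definition from the SAP is an assumption.

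**1. Dilution, by formula.** Let q be the share with baseline score below 9, r their chance of reaching 9 or more at Week 24 (the same in both arms), and p the response rate among those entering at 9 to 11. The rate in the planned population is

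p_all = (1 − q) × p + q × r.

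Because r is common to both arms, the risk difference is (1 − q) × (p_active − p_placebo). Assume p = 60% on placebo and 75% on active. The difference is then 15.0 points and the odds ratio is (0.75/0.25)/(0.60/0.40) = 2.00. With r = 0 and q = 30%:

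- placebo: 0.7 × 0.60 = 0.420
- active: 0.7 × 0.75 = 0.525
- difference: 10.5 points
- odds ratio: (0.525/0.475)/(0.420/0.580) = 1.53

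Power below is for a two-sided 0.05 comparison of two proportions. It assumes 78 active and 104 placebo, that is 65% of 120 and of an assumed 160 placebo participants after sharing.

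| q | Placebo % | Active % | Difference (points) | Odds ratio | Power as planned | Power, 9 to 11 only |
|---|---|---|---|---|---|---|
| 0% | 60.0 | 75.0 | 15.0 | 2.00 | 0.57 | 0.57 |
| 10% | 54.0 | 67.5 | 13.5 | 1.77 | 0.45 | 0.52 |
| 20% | 48.0 | 60.0 | 12.0 | 1.63 | 0.36 | 0.47 |
| 30% | 42.0 | 52.5 | 10.5 | 1.53 | 0.29 | 0.42 |
| 40% | 36.0 | 45.0 | 9.0 | 1.45 | 0.23 | 0.37 |
| 50% | 30.0 | 37.5 | 7.5 | 1.40 | 0.19 | 0.32 |

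If 5% of the low group respond in both arms, q = 30% still gives 10.5 points and an odds ratio of 1.52. With an odds ratio of 2.00 among those at 9 to 11 and placebo rates of 50% or 70%, q = 30% gives 1.63 or 1.42. The risk ratio stays at 1.25 when r = 0, since (1 − q) cancels, but the SAP's logistic model reports an odds ratio.

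**2. Does the planned adjustment repair it?** This was simulated with baseline bulbar scores of 3 to 11 weighted towards the upper end, integer declines that depend on delta-FRS, 40% slowing on active, and a 10% chance of a one-point gain. The model adjusted for ALSFRS-R total and delta-FRS; onset site, riluzole and edaravone were left out. About 35% started below 9, and 0.8% of them responded. Odds ratios come from one very large sample, and power from repeated samples of 182.

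| Analysis | Odds ratio | Power |
|---|---|---|
| Everyone below 12, total score and delta-FRS | 1.68 | 0.36 |
| Baseline 9 to 11 only, same covariates | 2.28 | 0.48 |
| Everyone below 12, baseline bulbar score added | 2.76 | 0.59 |

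Adjusting for the total score does not remove the attenuation, while adding the bulbar score recovers more power than restriction does. The three odds ratios condition on different things, so power is the fairer comparison.

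**3. Range.** A separate simulation assumed 60 active, 80 placebo, 40% slowing and 10 to 50% below 9, in eight scenarios. Power was about 0.17 to 0.52 as planned, 0.21 to 0.55 restricted to 9 to 11, and 0.30 to 0.68 with everyone kept and the bulbar score added. At a 40% share the three values were 0.29, 0.36 and 0.48. Restriction raised power in every scenario but added nothing once the covariate was in. With no drug effect, the rejection rate stayed at 0.04 to 0.05.

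**The case against.** The best defence is that this is a supplementary measure of absolute state, taken in a subset that the SAP uses for many endpoints. Baseline-relative endpoints in the same subset cover preservation of bulbar function without this defect: no or only a one-point decline, time to first one-point decline, and rate of change in the bulbar score. The loss also works against the drug. All of this stands, and it is why the point is minor.

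The size is also open. At a 10% share, the table shows power of 0.45 against 0.52, a small loss. The Master Protocol and M-SAP were not available, and a floor on the bulbar score there would change the point. The phrase in 6.5.5, "treatment group, baseline ALSFRS-R score, site of onset (any bulbar vs. non-bulbar"), is read here as the ALSFRS-R total, which is how 4.1 uses baseline ALSFRS-R in its cut-off of 36. If the bulbar score was meant, the text needs only clarification.

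Three stronger readings are tempting, and the documents do not support them:

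- **That participants below 9 cannot respond.** Scores fluctuate, and SAP 6.5.2 and 6.5.3 allow for improvement. These participants must improve to respond, which is rare only under assumptions of decline.
- **That the trial enriched for bulbar dysfunction.** The RSA adds no inclusion criteria; a score below 12 is an analysis subset.
- **That chance imbalance in the share below 9 creates an apparent drug effect.** With 60 and 80 participants, the SD of that imbalance is √(q(1 − q)(1/60 + 1/80)), which is 0.074 at q = 25% and 0.085 at q = 50%. At an assumed 63% response among those at 9 to 11, this moves the risk difference by about 5 points. Under randomisation, however, that variation is already within the ordinary standard error. It is not added bias and does not inflate type I error.

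**Conclusion.** The point holds as a minor loss of efficiency. The population and threshold in SAP 4.1 do not fit together well, and the covariates in 6.5.5 do not make up for it. The direction follows from the definitions alone, provided few participants below 9 cross the threshold: the risk difference shrinks by the factor 1 minus their share, the odds ratio is attenuated and power falls.

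The size depends on the share below 9, the response rates, the bulbar slope and the shared-placebo numbers, none of which the documents give. Across shares of 10 to 50%, the odds ratio of 2.00 assumed in the formula falls to between 1.77 and 1.40. A reader might infer that a positive result on this endpoint would be suspect, or that the main conclusions are at risk. Neither follows: the null rejection rate is held, and the endpoint lies outside the hierarchy of SAP 6.5.1.

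**What to change.** Preferred: in SAP 6.5.5, state that the model for this endpoint also includes the baseline ALSFRS-R bulbar domain (Q1-Q3) score. This keeps every participant and gave the highest power in the simulations. The cost is one more model term. The crude proportions by arm will still be diluted, because the covariate acts on the odds ratio and its test.

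Alternative: in SAP 4.1, define the population for this endpoint as FAS participants with a baseline bulbar score of 9, 10 or 11, and report the 0 to 8 group descriptively. This also removes the dilution from the reported proportions. The cost is a smaller denominator, although those removed carry little information on this endpoint.

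Either is a short wording change and should be settled before unblinding.
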